6.5 Withdrawal Criteria

Patients may voluntarily withdraw from the study at any time.

Patients who have their devices removed or have a suture placed to close the scleral channel, will be withdrawn from the study.

Patients who are not implanted with XEN during surgery will be withdrawn from the study and considered a screen failure. Investigators are recommended to follow the patient until they are stable.

The investigator will consider withdrawing a patient from the study early if any of the following criteria are met:

- Patient develops (or has an exacerbation of) a medical condition that, in the opinion of the investigator, compromises the patient's ability to participate in the study
- Patient is unwilling or unable to continue to comply with study procedures
- Patient is unwilling or unable to continue in the study

Whenever possible, the decision to withdraw a patient from the study or study treatment will be discussed with the sponsor.

7. Response Measures and Summary of Data Collection Methods

Detailed information on equipment and methodology to be used is provided in the Protocol Procedure Manual.

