6.1.3 Operative Visit (Day 1)

Patients must be scheduled for surgery within 60 days of screening. The following procedures must be performed prior to the implantation of study treatment:

- Evaluation of inclusion/exclusion criteria
- Medical history, surgical history, ophthalmic history, and ophthalmic surgical history, including presence of ocular pathology and concomitant ocular medications (both eyes)
- Concomitant medications (systemic and ophthalmic [both eyes]) and procedures
- AEs
- Urine pregnancy test (for females of childbearing potential)

The implantation procedure must be performed in an approved surgical suite or operating room using standard aseptic technique and standard ophthalmic surgical techniques to prepare the patient and the operative study eye. Preoperative and intraoperative surgical medications will be administered as customary for the investigator.

[figure not shown]
It is recommended that the target quadrant be the superior nasal quadrant, unless conjunctival scarring will inhibit bleb formation. If implantation is not possible in this quadrant, the order of preference for Gel Implant location is superior temporal, inferior nasal, and lastly inferior temporal.

A detailed description of the XEN surgical procedure is provided in the Protocol Procedure Manual. The general steps of the surgical procedure are as follows:

1. Standard ophthalmic surgery techniques must be used to prepare the patient and the eye. The target area must be pretreated with mitomycin C (see Protocol Procedure Manual for dosing and intraoperative application details).
2. Surgeons may use their standard of care to obtain access to the surgical quadrant. The needle of the sterile XEN Injector preloaded with the XEN Gel Implant is advanced through the peripheral cornea and across the anterior chamber (ie, *ab interno*) toward the targeted quadrant. Corneal entry will be at least 1 to 2 mm anterior to the limbus (ie, not at the limbus or behind it) to ensure proper angulation on the Gel Implant up and away from the iris. The Gel Implant will be placed through the center of the angle.
3. Once the needle is aligned with the desired entry point in the anterior chamber angle, the surgeon advances the needle in the anterior chamber angle and sclera until the surgeon is able to visualize the needle bevel as it exits the sclera into the subconjunctival space.

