4. The surgeon initiates release of the XEN Gel Implant by moving the slider of the XEN Injector. To deploy the Gel Implant, a forward movement of the blue slider at the center of the Injector delivers the Gel Implant and retracts the needle. The slider will stop at the end of its travel indicating that the procedure is complete.

Figure 6–1 provides diagrams of the steps required to complete the implantation procedure.

Figure 6–1 XEN Implantation Procedure

- a. The surgeon advances the needle through the trabecular meshwork and the sclera until the needle bevel can be visualized in the subconjunctival space.
- b. Once the needle is properly positioned, the Gel Implant can be released from the needle by the surgeon.

Following surgery, a protective shield or glasses will be applied over the operative eye. The patient will be instructed to keep the shield or glasses over the operative eye until the first follow-up visit and then, at bedtime, for at least a week.

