8.3.3 Other Effectiveness Analyses

8.3.4 Safety Analyses

Safety analyses will be performed using the implanted population. The number and percentage of patients reporting AEs will be tabulated regardless of causality. AEs, adverse device effects (ADEs), BCVA, line change in BCVA from baseline, biomicroscopic slit lamp, and ophthalmoscopy findings will be summarized by frequencies at each visit.

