## **6.0            PATIENT POPULATION**

The Implanted Population will include all patients implanted with XEN. The Implanted Population will be used for all primary and secondary effectiveness analyses and all safety analyses.

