## 10.3 OTHER EFFECTIVENESS ASSESSMENTS

## **11.0            SAFETY ANALYSES**

The safety analysis will be performed using the Implanted Population. Safety assessments include adverse events (AEs), XEN procedure and assessments, pregnancy test, and ocular parameters as determined through assessments of visual acuity, visual field, pachymetry, biomicroscopic slit lamp, gonioscopy, and ophthalmoscopic examinations.

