### **11.1            ADVERSE EVENTS**

Adverse events will be coded by system organ class and preferred term using the Medical Dictionary for Regulatory Activities, version 21.0 or newer.

An AE will be considered treatment-emergent adverse event (TEAE) if it started after the initiation of XEN implant related procedures.

An overall summary of subject incidences of TEAEs will be presented and will include experiencing the following:

- TEAE (ocular, non-ocular)
- Treatment emergent serious adverse event (TESAE) (ocular, non-ocular)
- TEAE with outcome of death (ocular, non-ocular)
- Study treatment (XEN) related TEAE (procedure related, device related)
- TEAE leading to study treatment discontinuation (XEN device removal)
- TEAE leading to study discontinuation

In general, the number and percent of patients in the Implanted Population reporting TEAEs will be tabulated by system organ class (SOC) in alphabetical order and by preferred term (PT) in descending order of incidence within the SOC, and further categorized by severity and causal relationship to the implant procedure or the device. If

more than 1 AE is coded to the same PT for the same patient, the patient will be counted only once for that PT using the greatest severity and strictest relatedness for the summarization by severity and relationship. These summaries will include:

- Non-ocular TEAEs by SOC, PT and severity grade
- Ocular TEAEs by SOC, PT and severity grade (SE, fellow eye)
- Non-ocular TEAEs by SOC and PT
- Ocular TEAEs by SOC and PT (SE, fellow eye)
- XEN procedure related TEAEs by SOC and PT
- XEN device related TEAEs by SOC and PT
- Incidence of common ( $\geq 5\%$  of patients) TEAEs by PT
- XEN procedure or device related adverse events occurring in  $\geq 2\%$  of the patients by PT
- Serious non-ocular TEAEs by SOC and PT
- Serious ocular TEAEs by SOC and PT (SE, fellow eye)
- TEAEs leading to XEN device removal by SOC and PT
- TEAEs leading to XEN device replacement by SOC and PT
- TEAEs leading to the study discontinuation by SOC and PT

Subject data listings will also be provided to support each summary table.

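### Cheap improvement: attempted-but-not-implanted patients are screen failures, and the supplied documents plan no safety table or listing for their procedure and device events

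*Protocol*

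**What the plan says.** **Status of the patient.** Protocol 6.5: "Patients who are not implanted with XEN during surgery will be withdrawn from the study and considered a screen failure".

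**Steps before the implant is released.** Protocol 6.1.3 lists the operation in order. In step 1, "The target area must be pretreated with mitomycin C". In step 2 the injector needle passes through the peripheral cornea and across the anterior chamber. In step 3, "the surgeon advances the needle in the anterior chamber angle and sclera". Only in step 4 is the device delivered: "The surgeon initiates release of the XEN Gel Implant by moving the slider of the XEN Injector".

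**Population for safety.** Protocol 8.3.4: "Safety analyses will be performed using the implanted population". SAP 6.0: "The Implanted Population will be used for all primary and secondary effectiveness analyses and all safety analyses". SAP 11.0: "The safety analysis will be performed using the Implanted Population". SAP 11.1 names the same population for the adverse event tables, and SAP 11.2 for the surgical assessment, which includes complications. The device-problem summary in SAP 11.3 names no population of its own but sits under the rule in 11.0.

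**Start of the treatment-emergent period.** SAP 11.1 counts an event as treatment-emergent "if it started after the initiation of XEN implant related procedures".

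**Outputs beyond the implanted.** Only SAP 7.0 (disposition) covers all screened patients: failures by reason and timing, the entry criterion not met, and a listing of exit status. SAP 4.0 places the output specifications in a separate document, which was not available.

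**The concern.** The SAP uses one rule to decide when an event counts and another to decide in whom it counts, and the two do not cover the same patients. The first begins during surgery. The second depends on how surgery ended. A patient who had mitomycin C pretreatment, corneal entry or scleral needle passage and then received no implant falls between them.

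Safety is a stated objective (Protocol 3.1, SAP 5.0) of a study that SAP 4.1.1 calls pivotal. The planned safety summary is conditional on successful placement, which is one outcome of the procedure being assessed. A complication that made the surgeon stop, or a malfunction that prevented placement with no second device placed, could be missing from the summaries meant to show such events. A reader would also not see how often an attempt failed.

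**Working it through.** **1. Tracing the outputs.** Take a patient in whom a XEN-specific step was started and no implant was placed.

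| Output | Population | Patient's events shown? |
|---|---|---|
| Treatment-emergent event tables, SAP 11.1 | Implanted | No |
| Event listings, SAP 11.1 | Tied to those tables | None planned |
| Surgical assessment and complications, SAP 11.2 | Implanted | No |
| Device problems, SAP 11.3 | Not named; implanted under 11.0 | No, by inference |
| Screening disposition, SAP 7.0 | All screened | Count, reason and timing only |
| Exit-status listing, SAP 7.0 | All screened | Exit status only |

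No row gives event term, severity or relationship to device or procedure.

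**2. Collection.** Adverse events are recorded from consent (Protocol 7.2, 11.3), serious events are reported to the sponsor (11.4), and device deficiencies are documented and reviewed (11.1.6). The data gap is therefore small; the gap is in planned reporting.

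**3. Size.** The plan gives no figure on this point. Its only design figure, a precision of ±0.145 with 50 patients, concerns effectiveness. It reproduces (25/50 has an exact interval of 0.3553 to 0.6447, half-width 0.1447) and is not affected. The 65 implanted patients come from SAP 14.0. The counts below are assumptions: k patients attempted but not implanted, x implanted patients with a given event, and m of the k with that event.

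Implanted over attempted = 65/(65 + k):
- k = 0: 65/65 = 100%
- k = 1: 65/66 = 98.5%
- k = 3: 65/68 = 95.6%
- k = 5: 65/70 = 92.9%

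Event rate among attempted = (x + m)/(65 + k), with exact (Clopper-Pearson) 95% intervals, for k = 3:

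| x | Implanted only | m = 0 | m = 1 | m = 3 |
|---|---|---|---|---|
| 0 | 0/65 = 0% (0 to 5.5%) | 0/68 = 0% (0 to 5.3%) | 1/68 = 1.5% (0.04 to 7.9%) | 3/68 = 4.4% (0.9 to 12.4%) |
| 2 | 2/65 = 3.1% (0.4 to 10.7%) | 2/68 = 2.9% (0.4 to 10.2%) | 3/68 = 4.4% (0.9 to 12.4%) | 5/68 = 7.4% (2.4 to 16.3%) |

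The m = 3 column puts the event in every failed attempt and is an extreme. In general (x + m)/(65 + k) exceeds x/65 only if m/k > x/65, so the rate can also fall.

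**4. Chance that it arises.** If a proportion q of attempts ends without an implant, the chance of at least one such patient by the time 65 are implanted is 1 − (1 − q)^65. For assumed q of 1%, 2%, 3% and 5% this is 48%, 73%, 86% and 96%.

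**The case against.** The strongest reply is that the population rule is explicit, is the same in both documents, and hides nothing from the sponsor. Every adverse event and device deficiency is still recorded and reported, and the number of failed attempts may be zero. All of that stands. It makes this an improvement to reporting and not an error.

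Further points stand in part:
- The separate output specifications may already contain such a listing. That cannot be checked, so the claim covers only the supplied documents.
- Eligibility is rechecked on the operative day (Protocol Table 1-1) and SAP 7.0 tabulates the timing of failure, so failures at surgery may be visible as a count. That count need not show whether a XEN step had begun, and it does not describe the event.
- The device-problem summary names no population. Reading it as implanted-only is an inference from SAP 6.0 and 11.0.
- A device released and removed in the same operation may count as implanted, because Protocol 6.5 treats removal separately from never being implanted.
- Protocol 6.1.3 does not give the order of mitomycin C and lens surgery. A complicated lens extraction could fall before or after the first XEN step.
- Nothing says that the surgical assessment form is completed for screen failures.

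Some stronger readings are tempting. A reader might infer that these events are lost, but Protocol 7.2 and 11 require their collection. A reader might infer that all difficult placements drop out. However, first attempts that fail and then succeed stay in (SAP 11.2.1 allows 1 to 6 scleral channels, and SAP 11.1 tabulates events leading to device replacement), and so do later explants. A reader might also infer that the safety profile is biased in the device's favour. The documents give no failed-attempt rate, so neither size nor direction can be computed.

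**Conclusion.** The point holds as a cheap improvement. By the plan's own rules, an event that meets the treatment-emergent definition can be left out of the safety outputs because of how the procedure ended, and the supplied documents plan no other safety output that would show it. This is a gap in reporting; the two documents do not contradict each other here.

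Its size is unknown. If every attempt ends in implantation, nothing changes. The percentages above rest on assumed counts and show only that, with about 65 patients, one or two such cases would be visible in a safety table. The conclusion also assumes that the unseen output specifications add no listing of this kind. Effectiveness analyses and sample size are not touched.

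**What to change.** In SAP 6.0 and 11:

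1. Keep the Implanted Population for all planned tables.
2. Define the initiation of XEN implant related procedures by a named surgical step from Protocol 6.1.3, so that it is clear when an attempt has begun.
3. State whether a device released and removed in the same operation counts as implanted.
4. Add one listing of adverse events and device problems for attempted-not-implanted patients, with term, severity, seriousness and relationship, and give the number implanted over the number attempted. Show which procedure was under way when surgery stopped, so that complications of lens surgery can be told apart from those of XEN.
5. Include surgical-complication items only where the surgical assessment form was completed for these patients.

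The cost is some SAP wording, one listing and one count. The adverse event and device-problem data are already collected. The attempted count needs the definition in item 2, and the documents do not show that a field recording a started attempt exists. The downsides are slightly more analysis work and possibly less favourable complication counts.

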7.1 Effectiveness Measures

Primary effectiveness measures will be assessed at all visits according to the schedule in [Table 1-1](#).

The primary effectiveness measure, IOP, will be measured using a Goldmann applanation tonometer. Examiners must perform all effectiveness IOP measurements at approximately the same time of day for a given patient throughout the study whenever possible. IOP must be completed prior to pachymetry, gonioscopy, and ophthalmoscopy.

The number of concomitant IOP-lowering medications following implantation will also be recorded.

7.2 Safety Measures

The following will be collected and recorded on the appropriate eCRF page(s):

- AEs: All AEs, from the moment the patient signs the Informed Consent Form, will be monitored and recorded in the patient's source documents. All events will be reported to the sponsor on an AE eCRF, including seriousness, severity, action taken and relationship to study treatment. If AEs occur, the first concern will be the safety of the study patient.

- Females of childbearing potential will have pregnancy tests performed. Pregnancy test kits will be provided by the site and will be administered according to the instructions provided with the tests.

Measures of ocular safety include:

Visual acuity: Visual acuity tests will be performed at all scheduled visits, as described in [Table 1-1](#). Manifest refraction using Snellen equivalent with a logMar chart (see Protocol Procedure Manual) will be performed at Screening, Baseline, Month 3, and Month 12/Exit. At all other visits, the visual acuity technician will use the last manifest refraction performed and determine the Snellen equivalent visual acuity using the logMar chart. If there is a 2-line or more reduction in visual acuity from the last BCVA performed, a repeat manifest refraction in both eyes and BCVA will be performed.

Pachymetry: Corneal thickness using ultrasound (contact) pachymetry will be performed on the central cornea. The same instrument will be used throughout the study for a given patient. Contact pachymetry will be performed after IOP measurement.

Visual field test: Visual field will be assessed using automated perimetry (using either Humphrey 24-2 full threshold program or SITA Standard). The same test methodology must be used throughout the entire study for a given patient.

Biomicroscopic slit lamp examination: Biomicroscopic examinations will be performed using a slit lamp. The examinations will include evaluation of the condition of the eyelids, conjunctiva (including assessment of bleb characteristics), cornea (including assessment for corneal stromal edema at the XEN Gel Implant location), anterior chamber, iris/pupil, and lens, and assessment of Gel Implant placement.

Gonioscopy: Iridocorneal angle assessments will include Shaffer grade; postoperative gonioscopy will include device displacement, malposition, movement, device contact with cornea and/or iris, and device tip occlusion.

Ophthalmoscopy: The stereoscopic fundus assessments will be conducted through a dilated pupil. Non-dilated ophthalmoscopy may be performed if the investigator believes that pupil dilation may put the patient at risk. The examinations will include evaluation of the macula, vitreous, and retina. The cup/disc ratio and presence of optic disc pathology will be determined using stereoscopic evaluation. When dilation is used, ophthalmoscopy should be the last examination.

7.3 Health Outcome Measures

The frequency of symptoms will be assessed using a modified version of the ocular symptom questionnaire designed for the collaborative initial glaucoma treatment study (CIGTS), which is referred to as the patient ocular symptoms questionnaire within this protocol.

All patients will be asked to complete the Patient Ocular Symptoms Questionnaire at screening and then again at Months 3, 6, and 12.

7.4 Summary of Methods of Data Collection

Electronic data capture using a validated electronic data capture system (EDC) will be used to collect study-specific information, such as patient and investigator assessments. The data will be entered on the eCRF in a timely manner on an ongoing basis. The investigator is responsible for ensuring that data are properly recorded on each patient's eCRF and related documents. An investigator who has signed the protocol signature page must review and personally sign for the eCRFs (as indicated in the eCRFs) to ensure that the findings are recorded on the eCRFs correctly and completely. The designated monitor will source-verify the data. Investigators will provide access to hospital files, medical records, and other source documents containing patient clinical/medical information.

8. Statistical Procedures

A separate statistical analysis plan will be prepared to provide specifications for all analyses. The plan will be finalized and approved prior to clinical database lock.

8.1 Analysis Populations

An analysis will be performed after all implanted patients have completed the 12-month visit or exited the study and the database has been locked.

Implanted population: The implanted population will include all patients implanted with XEN. This population will be used for all primary and secondary effectiveness analyses and all safety analyses.

8.2 Collection/Derivation of Primary and Secondary Effectiveness Assessments

The primary effectiveness measure, IOP, will be measured using a Goldmann applanation tonometer. The measurements will be collected using the masked examiner method described in the Protocol Procedure Manual. Additionally, the number of concomitant IOP-lowering medications following implantation will be recorded. To determine the number of concomitant IOP-lowering medications, fixed-combination medications will be counted as multiple medications. For example, Combigan will be counted as 2 medications. Any IOP measurements or medication counts collected following non-study surgical procedures for IOP control or device explant (ie, device failures) will be excluded from the analyses.

8.2.1 Primary Effectiveness Variable

The primary effectiveness endpoint is the proportion of patients achieving at least a 20% reduction from baseline Hour 0 IOP while on the same number or fewer IOP-lowering medications at Month 12 and is derived from the effectiveness variables: Hour 0 IOP percent change from baseline and the number of concomitant IOP-lowering medications. The Hour 0 IOP percent change from baseline is calculated as $100 * (\text{Hour 0 IOP change from baseline}) / \text{baseline Hour 0 IOP}$.

The number of concomitant IOP-lowering medications following implantation will be compared with the number prior to implantation.

8.2.2 Secondary Effectiveness Variables

The secondary effectiveness variables are Hour 0 IOP, the associated change from baseline, and the number of concomitant IOP-lowering medications.

8.2.3 Other Effectiveness Variables

Other effectiveness variables include diurnal IOP fluctuation, the associated change from baseline, the reason for device failure (such as non-study surgical procedures for IOP control or device explant), and the change in the number of concomitant IOP-lowering medications compared to baseline. Additional details regarding the definition of device failure will be included in the analysis plan.

